### 9.1.2. DAS28 (ESR)

DAS28(ESR) values will be listed and summarized by dose group and nominal time. Mean and median change from baseline versus time profiles by dose group will be plotted.

Statistical Analyses –Mixed Model with Repeated Measures–	
Endpoint(s)	

 
• Change from baseline in DAS28(ESR)
 
	
Model Specification	

 
• This endpoint will be analyzed using a MMRM approach.
 
• Analysis will include the following fixed effects: 
 
• Dose group as a categorical variable
 
• Visit as a categorical variable
 
• Baseline DAS28(ESR) as a continuous variable
 
• Dose-by-visit interaction.
 
• Visit-by-baseline interaction.
 
 
 
• An unstructured variance structure will be used to model the within-patient errors.
 
• Analyses will be done with the MIXED Procedure in SAS, using the Kenward-Roger option to estimate denominator degrees of freedom and standard errors.
 
	
Model Checking & Diagnostics	

 
• Refer to Appendix 8: Model Checking and Diagnostics for Statistical Analyses.
 
	
Model Results Presentation	

 
• Point estimates and their associated 95% CI will be calculated for the differences between each GSK3196165 dose group and Placebo (GSK3196165 – Placebo).
 
• The primary treatment comparison will be the contrast between treatments at week 12.
 
	

### 9.1.3. SDAI, CDAI and FACIT-Fatigue

SDAI, CDAI and FACIT-Fatigue scores will be listed and summarized by dose group and nominal time. Mean and median change from baseline versus time profiles by dose group will be plotted.

Statistical Analyses –Mixed Model with Repeated Measures–	
Endpoint(s)	

 
• Change from baseline in SDAI, CDAI and FACIT-Fatigue
 
	
Model Specification	

 
• This endpoint will be analyzed using a MMRM approach.
 
	

Statistical Analyses –Mixed Model with Repeated Measures–

 
Analysis will include the following fixed effects: 
 
Dose group as a categorical variable
 
Visit as a categorical variable
 
Baseline as a continuous variable
 
Dose-by-visit interaction
 
Visit-by-baseline interaction
 
 
 
An unstructured variance structure will be used to model the within-patient errors.
 
Analyses will be done with the MIXED Procedure in SAS, using the Kenward-Roger option to estimate denominator degrees of freedom and standard errors.
 

Model Checking & Diagnostics

 
Refer to Appendix 8: Model Checking and Diagnostics for Statistical Analyses.
 

Model Results Presentation

 
LSmeans for each dose will be presented along with the associated 95% CI.
 
Point estimates and their associated 95% CI will be calculated for the differences between each GSK3196165 dose group and Placebo (GSK3196165 – Placebo).
 

#### **9.1.4. Categorical DAS28 Response**

A good or moderate response will be combined to form the “responder” category. The number and percentage of responders will be presented. The difference of response rate from Placebo and the associated 95% CI will be calculated. The 95% CI will be based on normal approximation.

#### **9.1.5. DAS28 Remission**

The number and percentage of remission from Placebo will be presented. The difference of remission rate and the associated 95% CI will be calculated. The 95% CI will be based on normal approximation.

#### **9.1.6. Other endpoints**

The other endpoints as below will be listed and summarized by dose group and nominal time as well as changes from baseline. Changes from baseline in only CRP, ESR and HAQ-DI will be plotted by dose group, respectively.

- Swollen Joint Count (28 and 66)
- Tender Joint Count (28 and 68)
- Patient’s Assessment of Arthritis Pain
  - Current pain
  - Past week’s pain
- Patient’s Global Assessment of Disease Activity
- Physician’s Global Assessment of Arthritis

- CRP (in mg/L), ESR (in mm/hr)
- Health Assessment Questionnaire-Disability Index (HAQ-DI)

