4. STUDY DESIGN

4.1. Overall Design

- This is a randomized, double-blind, parallel group, 3 dosage level, placebo-controlled, Phase 1/2 study with the objective to assess pharmacokinetics, safety, tolerability and efficacy of GSK3196165 for 12 weeks, in combination with methotrexate (MTX), in Japanese subjects with active moderate-severe RA despite treatment with MTX.
- Approximately 40 subjects will be randomized into the study (10 subjects in each treatment groups).

Figure 1 Study Design

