5.1. Inclusion Criteria

A subject will be eligible for inclusion in this study only if all of the following criteria apply:

AGE
1. Age ≥ 20 years at the time of signing informed consent.
TYPE OF SUBJECT AND DIAGNOSIS INCLUDING DISEASE SEVERITY
2. Japanese RA subjects who meets ACR/EULAR 2010 RA Classification Criteria.
3. Functional class I, II or III defined by the 1992 ACR Classification of Functional Status in RA.
4. Disease duration of ≥ 12 weeks (time from onset of patient-reported symptoms of either pain or stiffness or swelling in hands, feet or wrists).
5. Swollen joint count of ≥ 4 (66-joint count) and tender joint count of ≥ 4 (68-joint count) at screening and at Day 1.
6. DAS28(CRP) ≥ 3.2 at screening.
7. C-Reactive Protein (CRP) ≥ 0.3 mg/dL at screening.
8. Must have previously received MTX (8-16 mg weekly) orally for at least 12 weeks before screening, with a stable and tolerated dose for ≥ 4 weeks prior to Day 1.
WEIGHT
9. Weight ≥ 40 kg.
SEX
10. Male or female subjects are eligible to participate so long as they meet and agree to abide by the contraceptive criteria detailed in Appendix 2 .
INFORMED CONSENT
11. Written informed consent prior to any of the screening procedures including discontinuation of prohibited medications.

OTHER SAFETY-RELATED
12. Willing to continue or initiate treatment with oral folic acid (5 mg/week) and be treated during the entire study (mandatory co-medication for MTX treatment).
13. $D_{LCO} \geq 60\%^{1)}_{predicted}$; forced expiratory volume in 1 second (FEV_1) $\geq 70\%_{predicted}$; forced vital capacity (FVC) $\geq 80\%_{predicted}$.
1) For subjects with D_{LCO} values $\geq 60\%$ to $< 70\%$, a baseline chest high-resolution computed tomography (HRCT) must be performed during the screening period, and it is recommended that the subject be reviewed by a local pulmonologist to exclude significant pre-existing respiratory disease.
14. No evidence of active or latent infection with Mycobacterium tuberculosis (TB), as defined by all of the following:
1) No history of active or latent TB infection irrespective of treatment status.
2) A negative T-spot test within 4 weeks of baseline (Day 1).

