**NOTES :**

- T = Table, F = Figure, L = Listing, Y = Yes display generated.
- Stats Analysis = Represents TFL related to any formal statistical analyses (i.e. modelling) conducted.
- Summary = Represents TFL related to any summaries (descriptive statistics) of the observed raw data.
- Individual = Represents FL related to any displays of individual subject observed raw data.

Biomarkers/pharmacodynamic endpoint values will be listed and summarized by dose group and nominal time. Mean and median versus time profiles by dose group will be plotted.

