## 9.3. Pharmacokinetic / Pharmacodynamic Analyses

A graphical PK/PD exploration will be conducted to complement the statistical dose-response analysis and to visualize the nature of the concentration-response correlation. A variety of graphs will be generated per subject and in overall, where GSK3196165 concentration is characterised by the individual values, and the response is characterised by the individual values of the pharmacodynamic markers or efficacy.

Pharmacokinetic and pharmacodynamic data from this study may be combined with historical data (e.g. BAROQUE) for the purpose of further exploratory analysis (including population pharmacokinetic and/or PK/PD modelling as appropriate) which may be reported separately from the main clinical study report.

- Linear scatterplot of change from baseline in PD values (free soluble GM-CSF, GM-CSF-GSK3196165 complex) at each visit versus GSK3196165 concentration values at corresponding visit
- Linear scatterplot of change from baseline in CRP levels at each visit versus GSK3196165 concentration values at corresponding visit
- Linear scatterplot of change from baseline in DAS28(CRP) measures at each visit versus GSK3196165 concentration values at corresponding visit

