
 
Reporting for tables, figures and formal statistical analyses : 
 
Planned time relative to dosing will be used in figures, summaries, statistical analyses and calculation of any derived parameters, unless otherwise stated.
 
The impact of any major deviation from the planned assessment times and/or scheduled visit days on the analyses and interpretation of the results will be assessed as appropriate.
 
 
 
Reporting for Data Listings: 
 
Planned and actual time relative to study drug dosing will be shown in listings (Refer to IDSL Statistical Principle 5.05.1).
 
Unscheduled or unplanned readings will be presented within the subject's listings.
 
Visits outside the protocol defined time-windows (i.e. recorded as protocol deviations) will be included in listings but omitted from figures, summaries and statistical analyses.
 
 
 

Unscheduled Visits

 
Unscheduled visits will not be included in summary tables, except for the Respiratory events and the laboratory items which may be re-tested.
 
Unscheduled visits will not be included in figures.
 
All unscheduled visits will be included in listings.
 

Reporting Standards	
Descriptive Summary Statistics	
Continuous Data	Refer to IDSL Statistical Principle 6.06.1
Categorical Data	N, n, frequency, %
Reporting of Pharmacokinetic Concentration Data	
Descriptive Summary Statistics	Refer to IDSL Statistical Principle 6.06.1 Assign zero to NQ values (Refer to GUI_51487 for further details)
Reporting of Pharmacokinetic Parameters	
Descriptive Summary Statistics (Log Transformed)	N, n, geometric mean, 95% CI of geometric mean, standard deviation (SD) of logged data and [between and or within] geometric coefficient of variation (CV b/w (%)) will be reported. [1] $CV_b (\%) = \sqrt{(\exp(SD^2) - 1) * 100}$ (SD = SD of log transformed data)
Parameters Not Being Log Transformed	T max
Graphical Displays	

 
Refer to IDSL Statistical Principals 7.01 to 7.13.
 
	

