2.19.	ITT	EFF_F3	Plot of Predicted (95%CI) Treatment Difference from Placebo in CDAI		SAC
2.20.	ITT	EFF_F3	Plot of Predicted (95%CI) Treatment Difference from Placebo in FACIT-Fatigue		SAC
Each Components of Composite endpoints					
2.21.	ITT	EFF_F3	Plot of Mean (95% CI) Change from Baseline in CRP Profiles		SAC
2.22.	ITT	EFF_F3	Plot of Median (Range) Change from Baseline in CRP Profiles		SAC
2.23.	ITT	EFF_F3	Plot of Mean (95% CI) Change from Baseline in ESR Profiles		SAC
2.24.	ITT	EFF_F3	Plot of Median (Range) Change from Baseline in ESR Profiles		SAC
2.25.	ITT	EFF_F3	Plot of Mean (95% CI) Change from Baseline in HAQ-DI score Profiles		SAC
2.26.	ITT	EFF_F3	Plot of Median (Range) Change from Baseline in HAQ-DI score Profiles		SAC

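### CRP, ESR and the biomarkers are displayed only on the raw scale in arms of about 10; if CRP is strongly skewed and falls, the plotted 95% CI for its mean change can under-cover, and adding log ratios to baseline is a cheap improvement

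*SAP*

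**What the plan says.** SAP 9.1.6 covers the component endpoints, including CRP in mg/L and ESR: "The other endpoints as below will be listed and summarized by dose group and nominal time as well as changes from baseline". It then adds "Changes from baseline in only CRP, ESR and HAQ-DI will be plotted by dose group, respectively".

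- **CRP and ESR figures (SAP 11.10.5).** Figure 2.21 is "Plot of Mean (95% CI) Change from Baseline in CRP Profiles". Figure 2.22 is the median with range, and Figures 2.23 and 2.24 are the ESR pair. Table 10 marks CRP and ESR for summaries and listings only, with no longitudinal model.
- **PD and safety biomarkers (SAP 9.2.1).** "Mean and median versus time profiles by dose group will be plotted". All of Table 11 sits under an untransformed heading, with no log block. The titles of Figures 5.1 to 5.8 mention no confidence interval.
- **PK/PD (SAP 9.3, Figure 6.2).** "Linear scatterplot of change from baseline in CRP levels at each visit versus GSK3196165 concentration values at corresponding visit".
- **Entry (Protocol 5.1, criterion 7).** "C-Reactive Protein (CRP) ≥ 0.3 mg/dL at screening", with no upper limit there or in Protocol 5.2.
- **Arm size (Protocol 4.1 and 9.2).** 40 randomised 1:1:1:1, about 10 per arm, set by feasibility.

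Elsewhere the plan does use logs. DAS28 takes ln(CRP + 1) and ln(ESR) (Protocol 7.6.5, SAP 11.5.4). PK parameters get geometric means with 95% CIs (SAP 11.4.3), and PK concentrations are plotted on linear and semi-log axes (SAP 7.1.3.2).

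**The concern.** CRP has a floor at entry (0.3 mg/dL × 10 = 3 mg/L) and no ceiling, so an arm of 10 can easily hold one subject far above the rest. If treatment acts roughly in proportion to the starting value, raw change scales with baseline. The subject with the highest baseline then weighs most in the arm mean and its interval, and sits farthest out on the raw-change axis of Figure 6.2.

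These displays are all the analysis that CRP and the biomarkers receive; no baseline-adjusted model is planned for them. Protocol 9.4.5.1 names CRP and MRP8/14 as examples of the markers to be related to exposure. What is at stake is how readable and reliable the pharmacodynamic evidence is. The primary PK and safety results and the secondary DAS28(CRP) analysis are not affected.

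**Working it through.** **Plan's own figure.** The plan states no precision for CRP or the biomarkers. Its only precision figure is Protocol Table 4, which confirms the arm size. The exact interval for r events in 10 runs from the beta quantile B(0.025; r, 11 − r) to B(0.975; r + 1, 10 − r). For r = 1, 2, 3 this gives 0.25–44.50%, 2.52–55.61% and 6.67–65.25%, which matches the table.

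**Invented arm, to show the mechanism.** Baselines are 4, 5, 6, 7, 8, 10, 12, 15, 20 and 80 mg/L (sum 167), and all halve.

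- Mean change = −83.5/10 = −8.35. SD = 11.39 and t(0.975, 9) = 2.262. Half-width = 2.262 × 11.39/√10 = 8.15, so the 95% CI is −16.5 to −0.2.
- The top subject supplies 40/83.5 = 48% of the change. Without that subject the mean is −43.5/9 = −4.83. The median of all 10 is −4.5.
- Suppose the top subject instead rises from 80 to 100. Mean = (−43.5 + 20)/10 = −2.35 (95% CI −8.2 to 3.5) and the median is −3.75. Geometric ratio = exp[(9 ln 0.5 + ln 1.25)/10] = 0.55 (0.45 to 0.67).

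One subject moves the mean from −8.35 to −2.35 and the median only from −4.5 to −3.75.

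**Coverage, setting A.** All CRP inputs are assumptions. ln(baseline) is normal with median 10 mg/L and SD s, cut off below 3 mg/L. ln(follow-up) = ln 10 + ρ(ln baseline − ln 10) + ln g + s√(1 − ρ²)Z, where g is the geometric ratio. There were 60,000 arms of 10. Interval: mean change ± 2.262 × SD/√10.

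| log-SD s | no change, ρ = 0.7 | halving, ρ = 0.7 | halving, ρ = 0.5 | largest subject's share of total absolute change (halving, ρ = 0.7, median) |
|---|---|---|---|---|
| 0.6 | 95.9% | 91.6% | not run | 26% |
| 0.8 | 96.6% | 89.8% | 91.1% | 30% |
| 1.0 | 97.1% | 87.2% | 89.5% | 33% |
| 1.2 | 97.4% | 85.0% | 87.5% | 36% |

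The log-ratio interval covers 94.9% to 95.1% throughout. That is by construction, because the data were simulated log-normal.

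**Coverage, setting B.** Median 8 mg/L, screening value at least 3 mg/L, visit noise log-SD 0.4, change log-SD 0.6, ratio 0.5 or 0.35. For log-SD 0.8 to 1.2, raw coverage is about 80% to 92%, lowest with the most skew and the larger fall. At log-SD 0.6 with a halving it is 94.8%.

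The two settings differ at log-SD 0.6 (91.6% and 94.8%), so the low-skew result depends on the model. The no-change column belongs to setting A, where baseline and follow-up have nearly the same distribution and the changes are close to symmetric. It should not be assumed for other models.

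**The case against.** The strongest reply is that the plan already guards against an outlying subject. Median figures are planned for CRP, ESR and all the biomarkers (2.22, 2.24, 5.2, 5.4, 5.6, 5.8), and every value is listed (Listings 56, 57, 61, 62). A reader might infer that only means are shown, or that one subject decides the result. The documents do not support that: it is true of the mean displays alone. What remains is that a median with range gives no interval for the centre, and the range is itself set by the extremes.

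A reader might also call the Figure 2.21 intervals wrong. That is not supported either. The documents give no CRP variance, median or correlation, and the SAP text does not state how the interval is built; a t-interval is assumed here. Coverage was nominal or slightly above it in some settings. The raw and log intervals also estimate different quantities, an arithmetic mean change and a geometric ratio. Only CRP was simulated, and since the biomarker figure titles carry no interval, the coverage point does not reach them.

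A third tempting reading is that a real halving of CRP would be missed. No between-arm CRP comparison is planned and no hypothesis is tested (SAP 2.4, 11.7), so no decision hangs on an interval excluding zero. DAS28(CRP), the secondary efficacy endpoint, already logs CRP and is modelled by MMRM.

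Finally, log ratios are not free: they need positive values and a rule near the assay limit.

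**Conclusion.** The point holds as a modest improvement to exploratory displays. No log-scale or ratio display is planned for CRP, ESR or the biomarkers, although the same SAP uses logs for PK parameters and within DAS28. If CRP is strongly right-skewed and falls on treatment, the interval in Figure 2.21 can under-cover, at about 80% to 92% for log-SD 0.8 to 1.2, and one subject can supply about 30% of an arm's total absolute change. With no change, or with less skew and a halving, coverage can be near nominal.

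These sizes rest on assumed log-normal CRP, a t-interval and 10 subjects per arm with data. They do not show that the planned intervals are in error in this trial. Sample size, the primary endpoints and the DAS28(CRP) analysis are unaffected.

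**What to change.** Keep all the planned raw, median and listed displays, and add the following to SAP 9.1.6, 9.2.1 and 9.3.

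- For CRP, ESR and the quantifiable PD and safety biomarkers, give the geometric mean ratio to baseline with a 95% CI by dose and visit, computed on the loge scale, beside Tables 2.35, 2.36, 5.2 and 5.4.
- Add log-ratio versions of Figures 2.21, 2.23, 5.3 and 5.7, and give Figure 6.2 a log ratio to baseline on the y-axis.
- State one below-limit rule for these log displays, for example half the limit, and report how many values were substituted. Reconcile it with the laboratory rule in SAP 11.5.3: with no decimal digits, a result reported as below 1 becomes 1 − 1 = 0, which has no logarithm. For ESR, SAP 11.5.4 already replaces 0 by 1 in DAS28(ESR), and the same convention could serve.
- Leave the GM-CSF–drug complex as values. It can be expected to be absent before dosing (an inference; the documents do not say so), so it would have no usable baseline ratio.

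The cost is SAP wording and a transformation in existing programs, with no new data. The real downside is that ratios for markers near the assay limit will depend on the substituted value.

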## 9.2. Pharmacodynamic and Biomarker Analyses

### 9.2.1. Overview of Planned Pharmacodynamic and Biomarker Analyses

The pharmacodynamic analyses will be based on the ITT population, unless otherwise specified.

Table 11 provides an overview of the planned pharmacodynamic and Biomarker analyses, with full details of data displays being presented in Appendix 10: List of Data Displays.

**Table 11 Overview of Planned Pharmacodynamic and Biomarker Analyses**

Endpoint / Parameter/ Display Type	Untransformed													
	Absolute						Change from Baseline							
	Stats Analysis			Summary		Individual	Stats Analysis			Summary		Individual		
	T	F	L	T	F	F	L	T	F	L	T	F	F	L
free soluble GM-CSF and soluble GM-CSF complexed to GSK3196165														
Values				Y	Y		Y				Y	Y		Y
MRP8/14, ARG8 neoepitope, YKL-40 and 14-3-3<math>\eta</math>.														
Values				Y	Y		Y				Y	Y		Y
IL-6, IL-1<math>\beta</math>, TNF<math>\alpha</math>, IL-17A and IL-17F														
Values				Y	Y		Y				Y	Y		Y
SP-D, KL-6 and cholestenolic acid														
Values				Y	Y		Y				Y	Y		Y
measurement of GM-CSF autoantibodies at baseline														
Values				Y			Y							

**NOTES :**

- T = Table, F = Figure, L = Listing, Y = Yes display generated.
- Stats Analysis = Represents TFL related to any formal statistical analyses (i.e. modelling) conducted.
- Summary = Represents TFL related to any summaries (descriptive statistics) of the observed raw data.
- Individual = Represents FL related to any displays of individual subject observed raw data.

Biomarkers/pharmacodynamic endpoint values will be listed and summarized by dose group and nominal time. Mean and median versus time profiles by dose group will be plotted.

## 9.3. Pharmacokinetic / Pharmacodynamic Analyses

A graphical PK/PD exploration will be conducted to complement the statistical dose-response analysis and to visualize the nature of the concentration-response correlation. A variety of graphs will be generated per subject and in overall, where GSK3196165 concentration is characterised by the individual values, and the response is characterised by the individual values of the pharmacodynamic markers or efficacy.

Pharmacokinetic and pharmacodynamic data from this study may be combined with historical data (e.g. BAROQUE) for the purpose of further exploratory analysis (including population pharmacokinetic and/or PK/PD modelling as appropriate) which may be reported separately from the main clinical study report.

- Linear scatterplot of change from baseline in PD values (free soluble GM-CSF, GM-CSF-GSK3196165 complex) at each visit versus GSK3196165 concentration values at corresponding visit
- Linear scatterplot of change from baseline in CRP levels at each visit versus GSK3196165 concentration values at corresponding visit
- Linear scatterplot of change from baseline in DAS28(CRP) measures at each visit versus GSK3196165 concentration values at corresponding visit

## 11. APPENDICES

Section	Appendix
RAP Section 5 : General Considerations for Data Analyses & Data Handling Conventions	
Section 11.1	Appendix 1: Time and Events
Section 11.2	Appendix 2: Assessment Windows
Section 11.3	Appendix 3: Treatment States & Phases
Section 11.4	Appendix 4: Data Display Standards & Handling Conventions 
 
• Study Treatment & Sub-group Display Descriptors
 
• Baseline Definitions & Derivations
 
• Reporting Process & Standards
 

Section 11.5	Appendix 5: Derived and Transformed Data 
 
• General, Study Population & Safety
 
• Efficacy
 
• Immunogenicity
 

Section 11.6	Appendix 6: Premature Withdrawals & Handling of Missing Data 
 
• Premature Withdrawals
 
• Handling of Missing Data
 

Section 11.7	Appendix 7: Multiple Comparisons and Multiplicity
Section 11.8	Appendix 8: Model Checking and Diagnostics for Statistical Analyses
Other RAP Appendices	
Section 11.9	Appendix 9: Abbreviations & Trade Marks
Section 11.10	Appendix 10: List of Data Displays

## 11.1. Appendix 1: Time & Events

### 11.1.1. Protocol Defined Time & Events

Procedures	Screening	Baseline		Treatment Period											FU	Last Visit	EW 
	Visit																
	1	2	3	4	5	6	7	8	9	10	11	12	13	14	15		
	Week																
	(up to 4 weeks)	0	1	2	3	4	6	8	10	12	15	18	22				
	Day																
Allowance		1	3*	8	15	22	29	43	57	71	74*	85	106	127	155		
Written Informed Consent(s)	X			±1 day				±3 days			±1 day	±3 days	±1 week				
Subject Demography	X																
Medical, Disease, Therapy History	X																
Inclusion/Exclusion Criteria	X																
Efficacy and PRO Assessments 																	
Swollen (66) & Tender (68) Joint Count 	X	X 		X	X		X	X	X			X				X	X
Patient's Assessment of Arthritis Pain, Patient's Global Assessment of Arthritis, Physician's Global Assessment of Arthritis 	X	X 		X	X		X	X	X			X				X	X
HAQ-DI 	X	X 		X	X		X	X	X			X				X	X
FACIT-Fatigue 		X 					X					X				X	X

